### 2.3 Trial rationale

A meta-analysis in China has shown a prevalence of haemophilia of 5.5 per 100,000 males (3.6 per 100,000 males and females) and about 16% of these suffer from haemophilia B. However, according to the WFH, a total of 2,460 patients with haemophilia B were registered in China in 2018, corresponding to 0.18 per 100,000 inhabitants. Thus, less than 1/3 of the anticipated number

of patients with haemophilia B in China are diagnosed and there is a large number of patients who are either undiagnosed or untreated.

With the rapidly improving standard of care in China, an increasing number of patients with haemophilia B in China are expected to be diagnosed and to be managed in the future.

Consequently, optimal prophylactic treatment needs to become more readily available to the patients. This will significantly increase the demand for FIX products in China in the future. Currently, there are no extended half-life rFIX products available in China. Therefore, Chinese patients still face the challenges associated with frequent and repeated i.v. injections.

The rationale for this phase 3b trial is to investigate the efficacy, safety and pharmacokinetics of nonacog beta pegol used for treatment of bleeding episodes and for prophylaxis in Chinese patients with moderate to severe haemophilia B (FIX activity  $\leq 2\%$ ) in order to enable a comparison of efficacy, safety and pharmacokinetic data from the current trial in Chinese patients with data from the global pivotal phase 3a trial with nonacog beta pegol (Trial NN7999-3747).

## 2.4 Benefit-risk assessment

Main benefits and risks are described in the below sections. More detailed information about the known and expected benefits and risks and reasonably expected adverse events of nonacog beta pegol may be found in the investigator's brochure.

### 2.4.1 Risk assessment

Potential risk of clinical significance	Summary of data/rationale for risk	Mitigation strategy
Trial treatment: Nonacog beta pegol		
Identified risks		
Allergic/hypersensitivity reactions	As with any intravenous product, allergic/hypersensitivity including anaphylactic reactions cannot be excluded. Allergic-type hypersensitivity reactions have been reported in patients treated with marketed FIX products. For results on allergic reactions reported in the nonacog beta pegol clinical trial programme, see Section 6.4.2.3 of the investigator's brochure. 	Patients are monitored carefully for allergic/hypersensitivity reactions. Patients are monitored carefully for anaphylactic reactions as defined by Sampson et al.  (see Section 10.3.3). Allergic/hypersensitivity/anaphylactic reactions must be treated as per local practice and as per investigator's discretion.
FIX inhibitors	The main safety issues identified with use of FIX products are immunogenicity and lack of efficacy due to formation of neutralising antibodies against FIX. See Section 7.2.1.1 of the investigator's brochure  for further details on identified risks, and Section 6.4.2.4 of the investigator's brochure  for results on inhibitor development in the nonacog beta pegol clinical trial programme.	For previously treated patients with no history of FIX inhibitor development, the risk of inhibitor formation is low. As per inclusion criterion no. 4 (see Section 5.1), only patients with a history of at least 100 EDs to products containing FIX are eligible. Also, exclusion criterion no. 4 excludes patients with a known history of FIX inhibitors (Section 5.2). If reduced efficacy from treatment is suspected, an assessment

Potential risk of clinical significance	Summary of data/rationale for risk	Mitigation strategy
	for FIX inhibitors should be performed (see Section 8.6.2 ).	
Trial treatment: Nonacog beta pegol (continued)		
Potential risks		
Thromboembolic events	
Thromboembolic events are considered an important potential risk considering the fact that supraphysiologically elevated procoagulant levels may be associated with an increased risk of venous thrombosis.
 
No thromboembolic events have been observed in the nonacog beta pegol clinical trial programme; see Section 6.4.2.3 of the investigator's brochure.
	Thromboembolic events are monitored closely.
Accumulation of polyethylene glycol (PEG) in the brain (choroid plexus) and in other tissues/organs after long-term treatment	
There has been no indication of PEG accumulation beyond steady state after nonacog beta pegol treatment non-clinically or clinically. The possible clinical consequences of potential PEG presence are currently unknown.
 
Potential effects of PEG accumulation are monitored closely.
	Long-term safety including potential effects of PEG accumulation in the choroid plexus and other tissues/organs are monitored in the clinical trials and post-marketing.
Trial procedures		
Intravenous (i.v.) injection	Wrong route of administration, e.g. intramuscular instead of intravenous.	Administration of trial product at sites are performed by trained staff. The previously treated patients and/or their caregivers have experience with i.v. injection and will be trained by site staff in use of the trial product.
Physical examination and body measurements	No risks are expected to be associated with standard physical examination. Burden (embarrassment, discomfort, distress) associated with examinations that are related to sexual development (e.g. in adolescents) can be expected.	As this assessment is performed by physicians familiar with the patient population, the burden is expected to be low.

Potential risk of clinical significance	Summary of data/rationale for risk	Mitigation strategy
Trial procedures (continued)		
Risk of COVID-19 infection in relation to participation in the trial	
Patients and caregivers may be exposed to the risk of COVID-19 transmission and infection in relation to site visits if an outbreak is ongoing in the country.
 
If a patient is tested positive for COVID-19.
	
The risk of COVID-19 transmission in relation to site visits is overall considered to be low. To minimise the risk as much as possible, the following measures have been taken: On-site visits will be well-prepared and as short as possible. Physical contact between patients and site staff will be limited to the extent possible, and protective measures will be implemented such as masks sanitizers etc.
 
The risk of COVID-19 transmission in relation to site visits is overall considered to be low. However, if a patient is tested positive for COVID-19, then the investigator must ensure proper medical care. If possible, site visits can be converted to telephone visits. If the patient recovers in time for the primary endpoint visit, then the investigator should encourage the patient to visit the site for the primary endpoint visit. All necessary precautions must be taken for the site visit.

## 2.4.2 Benefit assessment

Nonacog beta pegol has a longer half-life compared to standard FIX products. The longer half-life of nonacog beta pegol allows for PPX treatment with a reduced injection frequency and higher FIX activity trough levels, which subsequently will lead to better compliance with a prophylactic regimen and improved joint health. Furthermore, the prolonged effect of nonacog beta pegol allows on-demand treatment as well as surgical haemostatic coverage with a reduced frequency of dosing and duration of therapy as compared with other standard half-life FIX products. Thus, nonacog beta pegol has the potential to improve the quality of life for haemophilia B patients by offering a convenient treatment with a reduced treatment burden from less frequent injections.

## 2.4.3 Overall benefit-risk conclusion

No clinical safety issues have been identified that precludes further clinical development of nonacog beta pegol. AEs from the clinical trials that have been evaluated to be related to nonacog beta pegol are consistent with what has been observed, and what is expected, with use of other FIX products. The potential benefits of nonacog beta pegol are considered to outweigh the identified and potential risks.

Taking into account the measures taken to minimise risk to patients participating in this trial, the potential risks identified in association with use of nonacog beta pegol are justified by the anticipated benefits that may be afforded to patients with haemophilia B.

## 3 Objectives and endpoints

### 3.1 Primary and secondary objectives

#### Primary objective

- To evaluate the clinical efficacy of nonacog beta pegol in haemostasis (treatment of bleeding episodes during on-demand and prophylaxis [PPX]) in Chinese patients aged 12-70 years with moderate to severe haemophilia B

#### Secondary objectives

In Chinese patients aged 12-70 years with moderate to severe haemophilia B:

- To evaluate the clinical efficacy of nonacog beta pegol in PPX treatment (number of treated bleeding episodes during PPX)
- To evaluate the consumption of nonacog beta pegol
- To evaluate the immunogenicity of nonacog beta pegol
- To evaluate the general safety of nonacog beta pegol
- To evaluate the pharmacokinetic properties of nonacog beta pegol

### 3.2 Primary and secondary endpoints

#### 3.2.1 Primary endpoint

Endpoint title	Time frame	Unit
Haemostatic effect of nonacog beta pegol when used for treatment of bleeding episodes during on-demand and PPX	From start of treatment (week 0) until end of treatment (up to week 50)	Count

#### 3.2.2 Secondary endpoints

##### 3.2.2.1 Secondary efficacy endpoints

Endpoint title	Time frame	Unit
Number of treated bleeding episodes during PPX treatment (Arm B only)	From start of treatment (week 0) until end of treatment (week 50)	Count
Consumption of nonacog beta pegol for treatment of bleeding episodes	From start of treatment (week 0) until end of treatment (up to week 50)	IU/kg per bleed
Consumption of nonacog beta pegol for PPX treatment (Arm B only)	From start of treatment (week 0) until end of treatment (week 50)	IU/kg per year
FIX trough levels during PPX treatment (Arm B only)	From start of treatment (week 0) until end of treatment (week 50)	IU/mL

### 3.2.2.2 Secondary safety endpoints

Endpoint title	Time frame	Unit
Number of patients with inhibitory antibodies against FIX defined as titre $\geq 0.6$ Bethesda units (BU)	From start of treatment (week 0) until end of treatment (up to week 50)	Count
Number of adverse events (AEs)	From start of treatment (week 0) until end of treatment (up to week 50)	Count
Number of serious adverse events (SAEs)	From start of treatment (week 0) until end of treatment (up to week 50)	Count

### 3.2.2.3 Secondary pharmacokinetic endpoints

[figure not shown]
Endpoint title	Time frame	Unit
Incremental recovery (IR) (Arm B only)	Single-dose: 30±10 minutes post-injection at week 0 Steady-state: 30±10 minutes post-injection at week 12	(IU/mL)/(IU/kg)
Terminal half-life ( $t_{1/2}$ ) (Arm B only)	Single-dose: 0-168 hours post-injection at week 0 Steady-state: 0-168 hours post-injection at week 12	h
Clearance (CL) (Arm B only)	Single-dose: 0-168 hours post injection at week 0 Steady-state: 0-168 hours post injection at week 12	mL/h/kg
Area under the curve (AUC) (Arm B only)	Single-dose: 0-168 hours post injection at week 0 Steady-state: 0-168 hours post injection at week 12	h·IU/mL

## 4 Trial design

### 4.1 Overall design

This is a multi-centre, open-label phase 3b trial evaluating the clinical efficacy, safety and pharmacokinetics of nonacog beta pegol during on-demand and for prophylactic treatment in Chinese patients aged 12-70 years with haemophilia B and a FIX activity of  $\leq 2\%$ .

An overview of the trial design is given in [Figure 4-1](#).

a Including treatment of bleeds during the on-demand period as well as scheduled once-weekly PPX doses and treatment of breakthrough bleeds during the PPX period

b Both 50 EDs and 50 weeks in trial must be fulfilled for a patient to complete the trial

ED, exposure day; N, number of patients; PK, pharmacokinetics; PPX, prophylaxis; SD, single-dose; SS, steady-state; wks, weeks

**Figure 4-1 Overview of trial design**

A total of 30 patients will be included in the trial and a minimum of 24 patients must complete the trial. The trial will have two arms: Arm A (on-demand/PPX treatment arm) and Arm B (PPX treatment arm including single-dose and steady-state pharmacokinetic assessment). Patients will not be randomised to Arm A and Arm B. Whether a patient will be in Arm A or Arm B is the choice of the patient and the investigator and will be decided at the screening visit. A minimum of 12 patients in each of the two treatment arms must complete the trial.

In Arm A (on-demand/PPX), the on-demand treatment period will be 28 weeks. For a patient in Arm A, 30 EDs to nonacog beta pegol in the entire trial must be fulfilled to complete the trial (including treatment of bleeds during the on-demand period as well as scheduled once-weekly PPX doses and treatment of breakthrough bleeds during the PPX period).

In Arm B (PPX), 50 EDs to nonacog beta pegol (including treatment of breakthrough bleeds) and 50 weeks in trial must be fulfilled to complete the trial. One single-dose and one steady-state pharmacokinetic profile will be obtained in patients in Arm B. The single-dose pharmacokinetic profile will start at first dosing (Visit 2), while the steady-state pharmacokinetic profile will be obtained at Visit 5. The steady-state pharmacokinetic profile may be postponed but must be conducted between Visit 5 and Visit 9.

In both treatment arms, the screening period will be 2 weeks (+7 days) and the follow-up period will be 30 days (+5 days).

The duration of the trial for each individual patient will be up to 64 weeks, i.e. 2 weeks screening period, up to 58 weeks treatment period (only applicable in Arm A in case a patient has no or few bleeds during the trial) and 30 days follow-up period.

The clinical efficacy assessment of nonacog beta pegol in the treatment of bleeding episodes will be based on the treatment of all bleeding episodes in Arm A and Arm B (including specific information on target joints as defined at baseline). The haemostatic response to nonacog beta pegol will be assessed by the patient/caregiver using a four-point scale (excellent, good, moderate and none response) by counting excellent and good as success and moderate and none as failure. Amount and number of injections of nonacog beta pegol per bleeding episode will also be recorded.

Efficacy of prophylaxis treatment with nonacog beta pegol will be assessed by the number of spontaneous and traumatic treated bleeding episodes observed in Arm B (annualised bleeding rate will be estimated). In addition, trough levels of the surrogate efficacy parameter, FIX activity, will be evaluated (in Arm B only).

Major and minor surgery is allowed in the trial, and information on the haemostatic effect and consumption of nonacog beta pegol in relation to surgery will be collected as applicable.

The safety of nonacog beta pegol will be evaluated based on the following safety assessments: AEs, safety laboratory parameters, physical examination and vital signs.

The pharmacokinetics will be evaluated by measurement of plasma FIX activity in blood samples collected pre-dosing and 30 minutes, 8, 24, 48, 96 and 168 hours post-dosing. All patients will have FIX activity measurements pre-dosing and 30 minutes post-dosing at all dosing visits during PPX treatment and during surgery. The analysis of plasma FIX activity will be performed at a central laboratory in China selected by Novo Nordisk.

#### **4.1.1 Treatment of patients**

Patients will receive nonacog beta pegol as prophylaxis, as on-demand for treatment of bleeding episodes and in relation to surgery ([Table 4-1](#)).

The trial product is nonacog beta pegol (N9-GP) produced by Novo Nordisk. The trial product is a recombinant FIX product and is a sterile, freeze-dried powder in vials, which is reconstituted with histidine solvent for injection (see Section [6.1](#) for further details). Trial product will be administered as i.v. injections at home by the patient and/or caregiver, at the trial site, or in exceptional cases in another clinic/hospital. All patients should be trained in home treatment of nonacog beta pegol. In Arm A, the first two doses of the trial product should be administered at the trial site or at a hospital/clinic as agreed with the investigator under supervision of medically qualified personnel. In Arm B, the first two doses of the trial product should be administered at the trial site.

**Table 4-1 Treatment regimens**

Treatment regimen	Age (years)	Dose	Dose frequency
Prophylaxis	12-70 years	40 IU/kg	Once-weekly
Treatment of bleeds	12-70 years	Mild and moderate bleeds: 40 IU/kg Severe bleeds: 80 IU/kg Additional doses of 40 IU/kg can be given if there is no observed effect of the first dose.	When necessary
Surgery	12-70 years	At investigator's discretion (the following dosing guidelines can be used). Minor surgery: 40 IU/kg prior to the surgery. Additional doses can be given if needed. Major surgery: 80 IU/kg prior to the surgery. Two repeated doses of 40 IU/kg (in 1- to 3-day intervals) within the first week after surgery. Thereafter, the frequency of dosing may be extended to once weekly until bleeding stops and healing is achieved.	Pre-dose and when necessary

#### **4.1.2 Maximum dose and daily administration of nonacog beta pegol**

The maximum dose to be administered to a patient within 24 hours is 200 IU/kg, with a maximum individual dose of 80 IU/kg to be administered no more frequently than every hour. These doses are only relevant in case of trauma, severe bleeding or surgery.

#### **4.1.3 Prophylaxis**

During PPX treatment, one single bolus dose of 40 IU/kg nonacog beta pegol will be administered i.v. once weekly. If a dose for treatment of bleeding is taken, the next PPX dose should still be taken on the planned day.

Additional doses of nonacog beta pegol can be administered if a patient experiences a treatment-requiring bleeding episode (see Section [4.1.4](#)) or in case of surgery (see Section [4.1.5](#)).

If a bleeding episode occurs on a planned PPX dosing day before administration of the PPX dose, or if a bleeding episode extends into such a day, the bleeding episode must be treated with the full PPX dose (this dose should be recorded as treatment of a bleeding episode). The patient should always follow the original PPX dosing scheme unless a dose has already been given to treat a bleeding episode during the same day.

#### **4.1.4 Treatment of bleeding episodes**

A treatment-requiring bleeding episode is defined as a bleed that is treated with haemostatic drugs. If a patient experiences a treatment-requiring bleeding episode it must be treated as soon as it is identified. The investigator must always be contacted in case of a severe bleed and the patient should visit the site within 24 hours, or when possible. Mild/moderate bleeding episodes can be treated at home without contacting the site. Treatment should be started as soon as a bleed is identified.

For treatment of a mild or moderate bleeding episode, for example a joint bleed, a single dose of 40 IU/kg nonacog beta pegol i.v. should be administered. If there is no observed effect of 40 IU/kg,

the investigator should be contacted prior to administration of a second dose of 40 IU/kg. A severe bleeding episode should be treated immediately at home or at a local emergency room with 80 IU/kg, and the clinical site must be contacted immediately thereafter for further instructions or transport.

During PPX treatment periods, any dose used for treatment of a bleed must be recorded as treatment of bleed and not as a PPX dose. When the bleed has resolved (e.g. pain reduction and no increase in swelling), the patient can resume the PPX dosing regimen.

If a bleeding episode occurs on a planned PPX dosing day before administration of the PPX dose, or if a bleeding episode extends into such a day, the bleeding episode must be treated with the full PPX dose (this dose should be recorded as treatment of a bleeding episode). The patient should always follow the original PPX dosing scheme unless a dose has already been given to treat a bleeding episode during the same day.

If a haemostatic response cannot be achieved after 48 hours using adequate doses of nonacog beta pegol treatment when treating bleeding episodes, another FIX product may be used at the discretion of the investigator. The use of other FIX products will result in discontinuation of trial treatment.

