#### **Treatment groups and duration:**

The following trial product will be supplied by Novo Nordisk:

- nonacog beta pegol (N9-GP) 2000 IU/vial as a sterile, freeze-dried powder in a single-use vial of 2000 IU/vial to be reconstituted with 4 mL histidine solvent provided in a pre-filled syringe for i.v. injection.

During PPX treatment, one single bolus dose of 40 IU/kg nonacog beta pegol will be administered i.v. once weekly.

Bleeding episodes will be treated with i.v. injection of 40 IU/kg nonacog beta pegol (mild or moderate bleeds) or 80 IU/kg nonacog beta pegol (severe bleeds). Additional doses of 40 IU/kg can be given if there is no observed effect of the first dose.

Patients undergoing surgical procedures will receive trial product as bleeding preventive treatment according to standard practice at the clinical site and/or at the investigator's discretion. Guidance on assessments and dosing is included in a separate flowchart and in text sections.

The duration of the trial for each individual patient will be up to 64 weeks, i.e. 2 weeks screening period, up to 58 weeks treatment period (only applicable in Arm A in case a patient has no or few bleeds during the trial) and 30 days follow-up period.

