**Table 6-1 Investigational medicinal product provided by Novo Nordisk A/S**

Trial product name	Nonacog beta pegol (N9-GP) 2000 IU/vial (IMP, test product)	Histidine solution (Solvent)
Dosage form	Powder for solution for injection	Solvent for solution for injection
Route of administration	Intravenous	Intravenous
Dosing instructions	
Prophylaxis: 40 IU/kg once weekly.
 
Treatment of bleeds: Single dose of 40 IU/kg (mild or moderate bleeds) or 80 IU/kg (severe bleeds). Additional doses of 40 IU/kg can be given if there is no observed effect of the first dose.
 
Minor surgery (dosing guidelines): Single dose of 40 IU/kg prior to the surgery. Additional doses can be given if needed.
 
Major surgery (dosing guidelines): Single dose of 80 IU/kg prior to the surgery. Two repeated doses of 40 IU/kg (in 1- to 3-day intervals) within the first week after surgery. Thereafter, the frequency of dosing may be extended to once weekly until bleeding stops and healing is achieved.
	Not applicable
Packaging	Vial	Pre-filled syringe with scale label

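### The rule for a bleed on a planned prophylaxis day calls for the 40 IU/kg prophylaxis dose and does not except severe bleeds, whose first dose is 80 IU/kg (minor wording error)

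*Protocol*

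**What the plan says.** Protocol Section 4.1.3 defines the prophylaxis dose: "one single bolus dose of 40 IU/kg nonacog beta pegol will be administered i.v. once weekly". Sections 4.1.3 and 4.1.4 then carry the same rule for a bleed that begins on a planned PPX day before that day's dose, or that is still continuing when one begins: "the bleeding episode must be treated with the full PPX dose (this dose should be recorded as treatment of a bleeding episode". Neither section limits the rule by severity.

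The dose for a severe bleed appears in four places:

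- Synopsis: "40 IU/kg nonacog beta pegol (mild or moderate bleeds) or 80 IU/kg nonacog beta pegol (severe bleeds".
- Section 4.1.4: "A severe bleeding episode should be treated immediately at home or at a local emergency room with 80 IU/kg".
- Table 4-1: "Mild and moderate bleeds: 40 IU/kg Severe bleeds: 80 IU/kg".
- Table 6-1: "Single dose of 40 IU/kg (mild or moderate bleeds) or 80 IU/kg (severe bleeds".

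None of the four makes an exception for a planned PPX day.

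**The concern.** Two instructions apply to the same injection and give different amounts. The PPX-day rule is worded as an obligation, is the more specific of the two, and comes after the severe-bleed dose in Section 4.1.4. The severe-bleed dose is worded less strongly. The wording therefore does not settle the matter in favour of 80 IU/kg, although that is almost certainly what is meant.

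What is at stake is patient safety. Section 8.1.1.2 counts every neck, iliopsoas, retroperitoneal and intracranial bleed as severe, and in these an inadequate first dose matters most. Section 8.1.1 asks the patient or caregiver to begin treating a severe bleed as early as possible. Section 4.1.4 allows this at home and adds that "the clinical site must be contacted immediately thereafter for further instructions or transport". A layperson may therefore choose the first dose before speaking to a clinician.

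**Working it through.** The check is a comparison of the dosing statements. The only arithmetic is on doses.

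1. **Mild or moderate bleed on a planned PPX day.** The PPX-day rule gives 40 IU/kg and the bleed rule gives 40 IU/kg. There is no conflict.
2. **Severe bleed that has already had its 80 IU/kg and runs on into a planned PPX day.** The PPX-day rule gives 40 IU/kg, which is also the size of an additional dose in Table 4-1. There is no conflict over the first dose.
3. **Severe bleed whose first dose falls on a planned PPX day before the weekly dose.** The PPX-day rule gives 40 IU/kg and the severe-bleed rule gives 80 IU/kg. The ratio is 40/80 = 0.5, a shortfall of 80 − 40 = 40 IU/kg. This is the only case in conflict. It can arise in Arm B and in the PPX period of Arm A, but not in the on-demand period, which has no planned PPX days.

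Four places might have set an order of precedence, and none does:

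- The closing sentence of the PPX-day paragraph (4.1.3 and 4.1.4) waives the scheduled dose once a bleed dose has been given that day. It does not set the size of the bleed dose.
- Section 4.1.2 is a ceiling: "The maximum dose to be administered to a patient within 24 hours is 200 IU/kg", with single doses of at most 80 IU/kg. It permits 80 IU/kg in severe bleeding but does not require it.
- Section 6.6 (dose modification) only points back to Sections 4.1 and 4.3.
- Section 8.1.1 makes the investigator responsible for treating severe bleeds but names no dose.

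The SAP contains no dosing rule.

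**Frequency.** Only one day in seven is a planned PPX day, only the part of it before the dose counts, and only severe bleeds are affected, so the event should be rare. Section 2.2 gives an overall bleeding rate on weekly prophylaxis, but the documents give neither the share of bleeds that are severe nor the usual hour of the weekly dose. A probability would rest mainly on those two unknowns, so none is given here.

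**Effect on the analyses.** The haemostatic response and the IU/kg per bleed could each be affected for the few bleeds concerned. Both are descriptive summaries across all treated bleeds, and no hypothesis is tested. The injection is recorded as bleed treatment under either rule.

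**The case against.** The strongest reply is that no sensible reader would under-dose. The PPX-day paragraph is about recording the injection and avoiding a double dose. The severe-bleed dose is in the same section and is repeated in three other places. The rule does not say that only the PPX dose may be given, so a single 80 IU/kg injection could be said to contain it. Section 4.1.3 allows additional doses for a bleed. Section 4.1.2 allows repeat dosing as often as hourly in severe bleeding: even after a first 40 IU/kg, a further 80 IU/kg brings the total to 120 IU/kg, within the 200 IU/kg limit for 24 hours. The investigator must always be contacted for a severe bleed.

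Much of this stands. The intent is fairly clear and the safeguards are real. The containment reading is possible, but it is not what the sentence says: it names a dose, and that dose is 40 IU/kg. The safeguards also act mainly after the first injection, which the protocol lets the patient or caregiver give at home.

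Two further replies narrow the concern. Home dosing also relies on the written directions for use (Section 6.1) and the home treatment guide and training (Section 8.8). These are not available here, and nothing shows that they repeat the PPX-day rule. In addition, several kinds of severe bleed are hard to recognise without a clinician. If a patient gives 40 IU/kg because the severity was missed, this sentence is not the cause, since the same would happen on any other day.

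A reader might infer that the protocol directs patients with severe bleeds to take half a dose, or that under-dosing is likely during the trial. The documents support neither reading. They show two unreconciled instructions, with the 80 IU/kg dose stated four times, and they provide no basis for a probability.

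**Conclusion.** The inconsistency is real and narrow. For the first dose of a severe bleed on a planned PPX day before the weekly dose, the protocol gives both 40 and 80 IU/kg and does not say which prevails. Following the PPX-day rule to the letter halves the first dose. The remaining exposure is a bleed recognised as severe and treated at home before any clinician is involved.

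The point is minor: the case should be rare, the intent can be inferred, mitigation exists, and the primary and secondary analyses are not materially affected. It is still worth correcting, because the sentence is mandatory, the bleeds concerned can be life-threatening, and one clause removes the ambiguity. The finding that the two instructions conflict rests on the text alone and needs no assumption. The judgement that the case is rare is qualitative and cannot be turned into a figure from the documents.

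**What to change.** In both Section 4.1.3 and Section 4.1.4, add to the PPX-day sentence: *except that a severe bleed receives 80 IU/kg as its first dose on any day; this dose is recorded as treatment of a bleeding episode and replaces the PPX dose that day.* No separate rule is needed for a severe bleed that has already had its 80 IU/kg. If a further 40 IU/kg is then required, the total is 80 + 40 = 120 IU/kg, within the 200 IU/kg limit for 24 hours in Section 4.1.2.

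Check that the written directions for use and the home treatment guide agree with this wording.

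The cost is one clause in two places, with the ethics approval that Section 10.1.1 requires for amendments. It can go into the next protocol amendment. Visits, data collection, sample size and the SAP do not change.
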